12.4 Study treatment start and EOT

The following imputations of study treatment start and EOT are considered for assigning safety events and assessments to the treatment-emergent period and used for deriving efficacy variables with definitions requiring EOT date. It is not considered for derivation of exposure variables. Details for assigning safety events and assessments to the treatment-emergence period, as described in Section 5.5.1, apply.

Type of date/time	Date/time is incomplete	Date/time is missing
Study treatment start date	Maximum of lower limit and randomization date.	Randomization date
Study treatment start time	See missing.	0:00 or randomization time if study treatment start date (after imputation) is equal to randomization date.
EOT	Earliest between treatment start date + 756 days (108 weeks), the upper limit, EOS date, and Death date.	Earliest between treatment start date + 756 days (108 weeks), EOS date and Death date.

EOS = End of Study; EOT = End of Trial.

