5.1.5 Subject study treatment completion status

Subjects who complete study treatment as per protocol are those with a record in the eCRF ‘Maintenance Ponesimod/Teriflunomide’ form with reason for treatment end given as ‘Completed as per protocol’.

A subject is considered to have prematurely discontinued from the study treatment if:

- at least one reason (‘Study treatment stopped due to’) is reported on the eCRF form ‘Premature Discontinuation of Study Treatment’ and/or
- the reason for treatment end is documented as ‘Premature Permanent Discontinuation’ on the eCRF ‘Up-titration Ponesimod/Placebo’, ‘Up-titration Teriflunomide/Placebo’ or ‘Maintenance Ponesimod/Teriflunomide’

The date of treatment discontinuation is the last date study drug was taken [defined in Section 5.3.1]. In case of a (partially) missing discontinuation date, the date is imputed with the EOS date as defined in Section 5.1.6, or with the upper limit of the partial date if prior to EOS.

Reasons for premature discontinuation from study treatment are documented on the 'Premature Discontinuation of Study Treatment' eCRF with the following possible answers: 'Death', 'Lost to follow-up', 'Pre-specified study treatment discontinuation criteria', 'Subject decision' (further split into 'Tolerability related', 'Efficacy related', 'Other', or 'Not known'), 'Physician decision' (further split into 'Adverse event', 'Lack of efficacy / Treatment failure' or 'Other') or 'Sponsor decision' (further split into 'Study termination by sponsor' or 'Other'). Whenever 'Other' is selected, free text can be provided in addition. Both recorded levels for treatment discontinuation (e.g., 'Subject decision' as well as 'Tolerability related'), if pre-specified, are to be included in analyses, while any free text is not to be reported in tables, only listed. An additional category called 'Reason not provided' is defined for subjects where the reason is missing.

Subjects who have prematurely discontinued treatment are considered to have stayed in the study beyond safety follow-up if their EOS date is after EOT + 30 days. These subjects will be considered to have entered the PTOp beyond the safety follow-up period.

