5.1.6 Subject study completion status

A subject is considered to have completed the study as per the corresponding entry on the 'End of Study' eCRF ("Did the subject complete the study?" answered with "Yes"). All subjects not completing the study are considered to have prematurely discontinued the study.

Note: A subject who prematurely discontinued study treatment but completed the PTOp is considered to have completed the study according to the protocol.

The End-of-Study (EOS) date is defined as the 'Date of End of Study' collected on the end of study eCRF, unless a subject is lost to follow-up or dies, in which case 'Date of Last Contact' from the end-of-study eCRF or 'Date of Death' from Death eCRF are used. If missing, the last recorded visit date (i.e., the latest assessment date within any visit) is considered as the EOS date.

For subjects completing the 108 weeks of treatment and entering the extension study, the EOS visit should occur at the FU1 visit (scheduled 14–22 days after last drug intake), or at the abbreviated FU2 visit if available (scheduled 23–37 days after last drug intake). For subjects completing the 108 weeks of treatment and not entering the extension study, the EOS visit corresponds to the FU2 visit (scheduled 30–37 days after last drug intake). For subjects prematurely discontinuing study treatment, EOS is scheduled to be the Week 108 visit (Visit 14A – W108A – Week 108).

For subjects prematurely discontinuing the study, reasons for premature discontinuation from study are: ‘Death’, ‘Lost to follow-up’, ‘Subject decision’ (further split into ‘Withdrawal of consent’, ‘Tolerability related’, ‘Efficacy related’, and ‘Other’), ‘Physician decision’ (further split into ‘Adverse event’ and ‘Other’) or ‘Sponsor decision’ (further split into ‘Study terminated’ and ‘Other’). Whenever ‘Other’ is selected, free text can be provided in addition. An additional category ‘Reason not provided’ is defined for subjects where the reason is missing.

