3.2. Efficacy / Endpoints

Condition	Type	Identifier	Source/Instructions	Additional information expected?	Important PD
FSIQ-RMS symptoms domain not assessable at Week 108 (Visit 14 or 14A)	M	PD_MM.176	Monitor PD / e.g., symptoms domain not completed or completed less than 4 days		No
Week 108 (Visit 14 or 14A) MRI not performed as per study protocol	M	PD_MM.177	eCRF /		Yes

	TPL-100062 Protocol Deviation Code List
Protocol Number: AC-058B301 Acronym: OPTIMUM	

			e.g., not done or not repeated in case of unacceptable quality as per central overread, missing sequences, done < 14 days after treatment with corticosteroids	
Visit 14 (EOT) was not performed within 7 days after study drug discontinuation for a subject who completed 108 week-treatment as per study protocol.	P	PD_PP.179	eCRF	No
Visit 14 (EOT) was not performed within 7 days after study drug discontinuation for a subject who prematurely discontinued study treatment	P	PD_PP.180	eCRF	No
Any applicable follow-up visit not performed as per study protocol	M	PD_MM.181	eCRF / Monitor PD / e.g. done out of time-window, full instead of abbreviated Follow-up 2	No
Visit 14 (EOT) was not performed for a subject who prematurely discontinued study treatment	M	PD_MM.206	eCRF	Yes
Visit 14 (EOT) was not performed for a subject who completed 108 week-treatment as per study protocol	M	PD_MM.207	eCRF	Yes
Any applicable follow-up visit not performed	M	PD_MM.208	eCRF	Yes

4. Anytime during the study

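### A completely missing last-dose date is imputed to EOS or start + 756 days, so early stoppers followed in the PTOP have their off-drug time analysed as on-treatment (SAP 12.4)

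*SAP*

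**What the plan says.** SAP 12.4 imputes a completely missing EOT as "Earliest between treatment start date + 756 days (108 weeks), EOS date and Death date". For an incomplete EOT the list also includes the latest date compatible with what was recorded: "Earliest between treatment start date + 756 days (108 weeks), the upper limit, EOS date, and Death date". The result is "considered for assigning safety events and assessments to the treatment-emergent period" and is also "used for deriving efficacy variables with definitions requiring EOT date". One limit is stated: "It is not considered for derivation of exposure variables".

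SAP 5.1.5 has a parallel rule for the treatment discontinuation date: "In case of a (partially) missing discontinuation date, the date is imputed with the EOS date as defined in Section 5.1.6". It goes on to cap a partial date at its upper limit, but it has no 756-day cap.

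The study keeps early stoppers under observation. SAP 2.1 and 2.1.1 allow them to remain in the PTOP up to Week 108, and 5.1.6 adds: "For subjects prematurely discontinuing study treatment, EOS is scheduled to be the Week 108 visit". SAP 5.4.1 puts that visit at 108 weeks ± 7 days after randomization.

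A premature EOT visit is scheduled at discontinuation (Table 3). The attached deviation code list, section 3.2, records as a deviation the case "Visit 14 (EOT) was not performed within 7 days after study drug discontinuation for a subject who prematurely discontinued study treatment". Neither imputation rule uses this visit.

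**The concern.** EOS is a reasonable upper bound for the last dose only when it follows the last dose closely. For an early stopper in the PTOP the two can be well over a year apart. The rule ignores the fact that the subject is already documented as having stopped early.

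Several derivations depend on EOT:

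- the EOT + 7 supplementary analyses of ARR, FSIQ-RMS, CUAL and CDA
- the per-protocol exclusion after premature discontinuation (7.1.3)
- membership of the PTOP set (7.1.5.4)
- the EOT + 15 treatment-emergent window (5.5.1) and the AE observation time (5.5.2.1)

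With a falsely late EOT, relapses and adverse events that occur off drug, possibly on another disease-modifying therapy (DMT), are attributed to study treatment in these analyses.

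**Working it through.** **Plan's own figure.** 108 × 7 = 756 days, as 12.4 states.

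**Assumptions for the illustration.** Treatment starts on the day of randomization (Day 1), so start + 756 days is Day 757. No subject-level dates are given, so the stop days are hypothetical.

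**Formulas**

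- Imputed EOT = min(Day 757, EOS), with no death (12.4)
- End of the EOT + 7 window = min(EOT + 7, EOS) (5.4.1.2.1)
- End of the treatment-emergent observation time = min(EOT + 15, EOS) (5.5.2.1)
- In the PTOP set if EOS > EOT + 7 (7.1.5.4)

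**Date completely missing, EOS at Day 757.** The imputed EOT is Day 757, and both windows end at Day 757.

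| True last dose | Correct EOT + 7 end | Days added | Correct EOT + 15 end | Days added |
|---|---|---|---|---|
| Day 84 | 91 | 757 − 91 = 666 | 99 | 757 − 99 = 658 |
| Day 168 | 175 | 757 − 175 = 582 | 183 | 757 − 183 = 574 |
| Day 420 | 427 | 757 − 427 = 330 | 435 | 757 − 435 = 322 |
| Day 588 | 595 | 757 − 595 = 162 | 603 | 757 − 603 = 154 |

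**EOS elsewhere in its ± 7-day window.** For EOS at Day 750, 757 or 764 the imputed EOT is Day 750, 757 or 757. In all three cases min(EOT + 7, EOS) equals EOS, so the efficacy window covers the whole off-drug period.

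**Per-protocol cut-off.** Data are excluded from EOT + 7, which is Day 757, 764 or 764. That is never before EOS, so in effect nothing is removed.

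**PTOP set.** The condition EOS > EOT + 7 becomes 750 > 757, 757 > 764 or 764 > 764. All are false. With the true Day 168 it is true in each case.

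**Subject leaves the study earlier.** Stop at Day 168, EOS at Day 300: imputed EOT = min(757, 300) = Day 300. The EOT + 7 window ends at min(307, 300) = Day 300 instead of Day 175, which adds 300 − 175 = 125 days. The misclassification runs to the subject's own EOS.

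**Partial dates.** The upper limit bounds the error at about 30 days if only the day is missing, and at about 364 days if day and month are missing.

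**Share of an arm.** 1133 subjects randomized 1:1 is about 566 per arm. Assume all are followed to Day 757: 566 × 757 / 365.25 ≈ 1173 person-years. Each affected subject who stopped at Day 168 adds 582 / 365.25 = 1.59 years. One such subject adds 1.59 / 1173 ≈ 0.14%, and twenty add 31.87 / 1173 ≈ 2.7%. The counts of 1 and 20 are assumptions; the SAP gives none.

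**The case against.** The strongest reply is that the trigger is narrow. EOT is the latest end date across several study drug logs (5.3.1), and sites were to reconcile diaries and returned drug before entering actual intake (5.3). A completely missing EOT needs every log record to lack an end date, and nothing in the SAP shows that this happens. This stands, and it limits the size of the point.

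For safety, a late EOT also fits the SAP's inclusive conventions: a missing AE onset date counts as treatment-emergent, and missing severity as severe. That is a fair defence of counting events, but it has limits. The same date lengthens the observation time for AE rates, and an inclusive safety convention gives no reason to count off-drug relapses in the EOT + 7 efficacy analyses.

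Three stronger readings are tempting and are not supported:

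- *All early stoppers are carried to Week 108.* SAP 2.1 says only that they may remain. For subjects lost to follow-up, EOS is the last contact date (5.1.6), which need not be near Week 108.
- *The uncapped rule in 5.1.5 puts a completer's last dose up to 37 days late.* That rule belongs to the definition of premature discontinuation, whereas the 37-day gap in 5.1.6 concerns subjects who completed treatment. For early stoppers with an on-schedule EOS, 5.1.5 and 12.4 differ by at most 764 − 757 = 7 days.
- *The start of another DMT would be a safe bound for the last dose.* Study concomitant therapies include those ongoing at study start (5.2.5.2), so the bound could fall before the first dose. DMT use during treatment is also a coded deviation (PD_MM.088), so a DMT start does not prove that study drug had stopped.

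**Conclusion.** The point holds for documented premature discontinuers whose last-dose date is completely missing, or known only to the year, and who were followed after stopping. For a completely missing date, all off-drug time to EOS is classed as on-treatment: 162 to 666 excess days in the EOT + 7 window for stops between Day 588 and Day 84, given EOS at Day 757 and treatment start at randomization. With only the year known, the error is at most about a year. Where only the day is missing it is about a month at most and needs no action.

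A reader might infer that the primary result is at risk. It is not: the main primary and secondary analyses use data up to EOS, and 12.4 excludes exposure variables. What is exposed is the EOT + 7 and per-protocol analyses, the PTOP set and treatment-emergent safety. The number of such subjects is not given and is probably small, so this is a minor correction to the wording.

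**What to change.** In SAP 12.4, for subjects with documented premature discontinuation, add the date of the premature EOT visit, if it took place, to the candidate dates for both a missing and an incomplete EOT. If that visit is missing, which the code list foresees (PD_MM.206), use the first PTOP visit date as the back-up bound. Make 5.1.5 refer to 12.4, so that one rule governs the date.

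The cost is a few lines of SAP wording and a small programming change, using dates already collected. A small overestimate of time on drug remains. It is up to 7 days when the EOT visit is on time and longer when it is late. With the back-up it can reach about 12 weeks plus the visit window, because PTOP visits are 12-weekly.

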13 LIST OF SUMMARY TABLES, LISTINGS AND FIGURES

The list of summary tables, listings, and figures is stored in a separate document in Excel format.

- 2: Author for 'Type', 'Identifier', 'Source/Instructions'; Reviewer of the document.
- 3: Reviewer of the document.

	TPL-100062 Protocol Deviation Code List
Protocol Number: AC-058B301 Acronym: OPTIMUM	

1. Protocol Deviations Before Randomization

1.1. Informed Consent and Patient Rights

Condition	Type	Identifier	Source/Instructions	Additional information expected?	Important PD
No informed consent form (ICF) signed	M	PD_MM.001	Monitor PD / To be reported even if subject is not randomized		Yes
Informed consent form signed after first study procedure	M	PD_MM.106	Monitor PD / Subject number assignment excluded - not a procedure		Yes
Informed consent procedures conducted by a non-qualified person	M	PD_MM.107	Monitor PD		Yes
During pre-randomization period, new ICF version not signed at first applicable protocol scheduled visit	M	PD_MM.143	Monitor PD		Yes
DLco addendum to ICF not signed or signed after initiation of DLco sub-study mandated procedure	M	PD_MM.003	Monitor PD		Yes
MRI addendum to ICF not signed or signed after initiation of supplementary MRI sub-study mandated procedure	M	PD_MM.004	Monitor PD		Yes
PPQ addendum not signed or signed after initiation of PPQ sub-study mandated procedure	M	PD_MM.108	Monitor PD		Yes
Other violations of Informed consent procedures for any sub-study	M	PD_MM.109	Monitor PD		No

1.2. General Eligibility

Condition	Type	Identifier	Source/Instructions	Additional information expected?	Important PD
-----------	------	------------	---------------------	----------------------------------	--------------

		TPL-100062 Protocol Deviation Code List		
Protocol Number: AC-058B301				
Acronym: OPTIMUM				
Randomization performed without taking into account centrally provided quality review (i.e. MRI, spirometry)	M	PD_MM.113	Monitor PD	No
Randomization performed based on local laboratory results	M	PD_MM.114	Monitor PD	No
Any pre-randomization safety assessment required for eligibility not performed prior to randomization	M	PD_MM.112	eCRF / Monitor PD / i.e. Blood pressure, Ophthalmological exam, OCT, Lab samples, Pregnancy tests, ECG, Spirometry	Yes
Any pre-randomization assessment not required for eligibility not performed prior to randomization	M	PD_MM.044	eCRF / Monitor PD / e.g., Weight, Physical exam, Body temperature, Urinalysis, eC-SSRS, Smoking status, Concomitant medications (ACL)	No
Pre-randomization assessments not performed using centrally provided devices	M	PD_MM.115	Monitor PD / e.g., ECG, spirometry	No
Subject re-screened without sponsor approval	M	PD_MM.186	Monitor PD / GCS&E input	No
Any pre-randomization safety assessment required for eligibility performed, but with at least one repeated assessment or test missing	M	PD_MM.042	eCRF / Monitor PD / e.g., V1 and V3 ECG confirming eligibility but V2 ECG not done; INR V1 available and V2 result unavailable	No
Any pre-randomization safety assessment required for eligibility performed, but results not available at randomization (subject retrospectively eligible)	M	PD_MM.188	eCRF / Monitor PD / e.g., Lab results available after randomization and confirming eligibility	No
Any pre-randomization assessment required for eligibility not performed as per study protocol and not covered by another PD code	M	PD_MM.187	eCRF / Monitor PD	No
Pre-randomization EDSS not performed according to study protocol or performed after randomization	M	PD_MM.209	eCRF / Monitor PD / Includes assessments not done;	Yes
Pre-randomization MRI not performed according to study protocol or performed after randomization	M	PD_MM.210	eCRF / Monitor PD / Includes assessments not done;	Yes

	TPL-100062 Protocol Deviation Code List
Protocol Number: AC-058B301 Acronym: OPTIMUM	

Pre-randomization FSIQ-RMS not performed according to study protocol or performed after randomization	M	PD_MM.211	MRI not repeated in case of unacceptable quality as per central overread, missing sequences eCRF / Monitor PD / Includes assessments not done; e.g., symptoms domain not completed or completed less than 4 days, impact domain not completed	No
---	---	---------------------------	---	----

1.3. Inclusion Criteria

Condition	Type	Identifier	Source/Instructions	Additional information expected?	Important PD
Age <18 or >55 at Visit 1 (Screening)	P	PD_PP.005	eCRF		Yes
Woman of childbearing potential (WOCBP) without negative serum pregnancy test at Visit 1 (Screening) or negative urine pregnancy test at Visit 2 (Baseline)	P	PD_PP.009	eCRF		Yes
WOCBP not agreeing to undertake 4-weekly urine pregnancy tests during the study and up to 6 weeks after the first of two tests showing teriflunomide plasma level < 0.02 mg/L	P	PD_PP.010	eCRF		Yes
WOCBP not agreeing to use reliable methods of contraception from Visit 1 (Screening) until 6 weeks after the first of two tests showing teriflunomide level < 0.02 mg/L	P	PD_PP.011	eCRF		Yes
Fertile male subjects not agreeing to use a condom during the treatment period and for an additional 6 weeks after the first of two tests showing teriflunomide level < 0.02 mg/L	P	PD_PP.012	eCRF		Yes
Subject presenting no diagnosis of MS as defined by revised (2010) McDonald Diagnostic Criteria for MS or with no relapsing course from onset (no diagnosis of RRMS or SPMS with superimposed relapses)	P	PD_PP.013	eCRF		Yes

	TPL-100062 Protocol Deviation Code List
Protocol Number: AC-058B301 Acronym: OPTIMUM	

No active disease as required per study protocol inclusion criterion 5	P	PD_PP.014	eCRF	Yes
Subject not assessed as ambulatory on EDSS or with EDSS > 5.5 at Visit 1 (Screening) or Visit 2 (Baseline)	P	PD_PP.016	eCRF	Yes
Not agreeing to use an accelerated elimination procedure for teriflunomide after last dose of study drug	P	PD_PP.017	eCRF	Yes

1.4. Exclusion criteria

Condition	Type	Identifier	Source/Instructions	Additional information expected?	Important PD
Lactating or pregnant woman	P	PD_PP.018	eCRF		Yes
Subject wishing to parent a child during the study	P	PD_PP.019	eCRF		Yes
Evidence of a relapse of MS with onset date < 30 days prior to baseline EDSS or between baseline EDSS and randomization	P	PD_PP.020	eCRF		Yes
Diagnosis of MS with progressive course from onset (i.e. diagnosis of primary progressive MS or progressive relapsing MS)	P	PD_PP.047	eCRF		Yes
Treatment within 7 days prior to randomization with IFN b-1a, IFN b-1b or glatiramer acetate	P	PD_PP.021	eCRF		Yes
Treatment within 15 days prior to randomization with b-blockers, diltiazem, verapamil, digoxin or any other anti-arrhythmic or HR lowering systemic therapy, cholestyramine or activated charcoal	P	PD_PP.022	eCRF		Yes
Treatment within 30 days prior to randomization with adrenocorticotrophic hormone (ACTH), systemic corticosteroids, dimethyl fumarate or vaccination with live vaccines	P	PD_PP.023	eCRF		Yes
Treatment within 90 days prior to randomization with medication listed in study protocol exclusion criterion 8	P	PD_PP.024	eCRF		Yes
Treatment within 180 days prior to randomization with medication listed in study protocol exclusion criterion 9	P	PD_PP.025	eCRF		Yes

	TPL-100062 Protocol Deviation Code List
Protocol Number: AC-058B301 Acronym: OPTIMUM	

Treatment within 24 months prior to randomization with lymphocyte-depleting biological agents (e.g. rituximab or ocrelizumab) or cladribine	P	PD_PP.026	eCRF	Yes
Treatment at any time prior to randomization with alemtuzumab, mitoxantrone, leflunomide, teriflunomide, fingolimod, ponesimod or other investigational S1P modulators, stem-cell transplantation	P	PD_PP.027	eCRF	Yes
Any infection or infection risk as per exclusion criteria 12, 13 and 14	P	PD_PP.028	eCRF	Yes
Known Progressive Multifocal Leukoencephalopathy (PML) infection / evidence of new neurological symptoms / MRI signs within 6 months prior to randomization compatible with a PML infection diagnosis	P	PD_PP.110	eCRF	Yes
Any malignancy as per exclusion criteria 15 and 16	P	PD_PP.029	eCRF	Yes
Presence of macular edema	P	PD_PP.030	eCRF	Yes
Any cardiovascular condition as per exclusion criterion 18	P	PD_PP.031	eCRF	Yes
Type 1 or 2 diabetes poorly controlled according to investigator's judgment, or diabetes complicated with organ involvement such as nephropathy or retinopathy	P	PD_PP.032	eCRF	Yes
Any clinically significant pulmonary condition as per exclusion criterion 20	P	PD_PP.033	eCRF	Yes
Active or latent TB, except if there is documentation of a previous adequate treatment for latent TB infection or TB disease	P	PD_PP.034	eCRF	Yes
Any hematology abnormal laboratory value at Visit 1 (Screening) or Visit 2 (Baseline) as per exclusion criterion 22	P	PD_PP.035	eCRF	Yes
Any hepatic condition as per exclusion criteria 23, 24 and 25	P	PD_PP.036	eCRF	Yes
Any abnormal liver laboratory value as per exclusion criterion 26	P	PD_PP.037	eCRF	Yes
Any renal condition as per exclusion criteria 27 and 28	P	PD_PP.038	eCRF	Yes
Any other category as per exclusion criteria 29, 30, 31,32 and 33	P	PD_PP.039	eCRF	Yes
Any contraindication for MRI as per exclusion criterion 34	P	PD_PP.040	eCRF	Yes

	TPL-100062 Protocol Deviation Code List
Protocol Number: AC-058B301 Acronym: OPTIMUM	

Unlikely to comply with study protocol as per exclusion criterion 35	P	PD_PP.041	eCRF	Yes
--	---	---------------------------	------	-----

